11.2 Study Monitoring

The contract research organization (CRO), on behalf of the Sponsor of this study, is responsible for ensuring that the study is conducted in accordance with ICH GCP and regulatory requirements. For this purpose, monitors will provide remote monitoring for this study. A site initiation visit will be conducted prior to beginning the study, and monitoring will be conducted at initiation, during and at closeout of the study. During the course of the study monitors will visit (virtual visit permissible) the clinical site at intervals to verify compliance to the protocol; completeness, accuracy, and consistency of the data and study product accountability; and adherence to ICH GCP and applicable regulations. As needed and when appropriate, the monitors will also provide clarification and additional training to help the site resolve issues identified during the monitoring visit.

Investigators and/or their study staff will be trained on the study protocol and all applicable study procedures prior to study initiation.

Study progress will be monitored by sponsor study team or representative (e.g., a CRO) as frequently as necessary to ensure the rights and well-being of study participants are protected; to verify adequate, accurate and complete data collection; protocol compliance and to determine that the study is being conducted in conformance with applicable regulatory requirements. Arrangements for monitoring visits will be made in advance in accordance with the monitoring plan.

13. ANNEX

ANNEX TO THE MASTER PROTOCOL

COUNTRY: BANGLADESH

Sample size and vaccination schedule

Approximately **720** participants aged 6 weeks old (42-47 days) will be enrolled in Bangladesh for this multi-country, multi-center, randomized, controlled, extended phase III study. The routine vaccine co-administered with the investigational vaccine include Adsorbed Diphtheria-Tetanus-whole cell Pertussis-Hepatitis B and Haemophilus influenza type b conjugate vaccine (DTP-HepB-Hib) and Pneumococcal Conjugate Vaccine, 10 valent (PCV10) in accordance with the local routine vaccination schedule. The vaccination schedule in Bangladesh is shown as followings:

Groups	Vaccination schedule					
	6 weeks	8 weeks	10 weeks	12 weeks	14 weeks	16 weeks
Group C1 & C2	sIPV DTP-HepB-Hib PCV10		sIPV DTP-HepB-Hib PCV10		sIPV DTP-HepB-Hib PCV10	
Group S1	sIPV	DTP-HepB-Hib PCV10	sIPV	DTP-HepB-Hib PCV10	sIPV	DTP-HepB-Hib PCV10
Group S2	DTP-HepB-Hib PCV10	sIPV	DTP-HepB-Hib PCV10	sIPV	DTP-HepB-Hib PCV10	sIPV

Enrollment requirements in terms of safety

Additionally, in one of the study countries, i.e., Bangladesh, after the initial 50 participants' enrollment, the further enrollment will be hold on, until the DSMB's approval based on their review conclusion on the safety data of the initial 50 participants within one month after their first vaccination.

ANNEX TO THE MASTER PROTOCOL

COUNTRY: PAKISTAN

Sample size and co-administration routine vaccines

Approximately **720** participants aged 6-8 weeks old (42-56 days) will be enrolled in Pakistan for this multi-country, multi-center, randomized, controlled, extended phase III study. The routine vaccine co-administered with the investigational vaccine include Adsorbed Diphtheria-Tetanus-whole cell Pertussis-Hepatitis B and Haemophilus influenza type b conjugate vaccine (DTP-HepB-Hib) and Pneumococcal Conjugate Vaccine, 13 valent (PCV13) in accordance with the local routine vaccination schedule, and rotavirus vaccine. The vaccination schedule in Pakistan is shown as followings:

Groups	Vaccination schedule					
	6 weeks	8 weeks	10 weeks	12 weeks	14 weeks	16 weeks
Group C1 & C2	sIPV DTP-HepB-Hib PCV13 Rotavirus vaccine		sIPV DTP-HepB-Hib PCV13 Rotavirus vaccine		sIPV DTP-HepB-Hib PCV13	
Group S1	sIPV	DTP-HepB-Hib PCV13 Rotavirus vaccine	sIPV	DTP-HepB-Hib PCV13 Rotavirus vaccine	sIPV	DTP-HepB-Hib PCV13
Group S2	DTP-HepB-Hib PCV13 Rotavirus vaccine	sIPV	DTP-HepB-Hib PCV13 Rotavirus vaccine	sIPV	DTP-HepB-Hib PCV13	sIPV

LLoQ	Lower Limit of Qualification
LOCF	Last Observation Carried Forward
MedDRA	Medical Dictionary for Regulatory Activities
PN	Preferred Name
PPS	Per Protocol Set
PRN	Pertactin
PT	Preferred Term
PT	Pertussis Toxin
SAE	Serious Adverse Event
SAP	Statistical Analysis Plan
SARS-COV-2	Severe Acute Respiratory Syndrome-Coronavirus
SCR	Seroconversion Rate
SDTM	Study Data Tabulation Model
sIPV	Strain Inactivated Poliovirus Vaccine
SOC	System Organ Class
SPR	Sero-protection Rate
SS	Safety Set
TEAE	Treatment Emergent Adverse Event

ULoQ	Upper Limit of Qualification
WHODrug	World Health Organization Drug Dictionaries

2 Introduction

2.1 Preface

This document presents the Statistical Analysis Plan (SAP) for “A Multi-country, Multi-center, Open-labelled, Randomized, Controlled, Extended Phase III Clinical Trial to Evaluate the Immunogenicity and Tolerability of Sabin Strain Inactivated Poliovirus Vaccine Administered with or without Routine Infant Vaccines”, which provides the details of methods to analyze baseline characteristics, immunogenicity and safety.

This SAP will be finalized and approved before the database is locked, and the programming of the corresponding statistical analysis will be completed until the database is locked.

Mockup Shell will be provided as an attachment of this SAP.

2.2 Purpose of Analysis

The purposes of the planned analysis described in this SAP are to evaluate the safety and immunogenicity of Sabin Strain Inactivated Poliovirus Vaccine(sIPV) administered with or without routine infant vaccines. The analysis results will be included in the Clinical Study Report (CSR), and may also be utilized for regulatory submissions, publications or others.

Additional analysis for other purposes, such as regulatory needs or sponsor requests, are not described in this SAP. If it occurs, the additional analyses are not included in the final CSR, but will be detailed in the document which presents the additional results.

2.3 Changes to Planned Analyses

The statistical analysis planned in this SAP is consistent with the ones in the protocol.

3 Objectives

3.1 Primary Objectives

- (1) To evaluate the non-inferiority of immune response to polio vaccination, when administered concomitantly with routine vaccines.
- (2) To evaluate the safety in terms of Adverse Reactions (ARs) (Vaccine-related Adverse Events (AEs)).

3.2 Secondary Objectives

- (1) To evaluate non-inferiority of immune response to diphtheria and tetanus antigens, when routine vaccines are administered concomitantly with sIPV.
- (2) To evaluate non-inferiority of immune response to acellular pertussis antigens, when routine vaccines are administered concomitantly with sIPV.
- (3) To evaluate other immunogenicity against diphtheria, tetanus, acellular pertussis antigens.
- (4) To evaluate other immunogenicity of sIPV, when administered concomitantly with routine vaccines.
- (5) To evaluate the immunogenicity against hepatitis B and Hib, when routine vaccines are administered concomitantly with sIPV.
- (6) To evaluate the immunogenicity against pneumococcal, when routine vaccines are administered concomitantly with sIPV.
- (7) To evaluate other safety in terms of ARs (Vaccine-related AEs).
- (8) To evaluate the safety in terms of Serious Adverse Events (SAEs).

4 Study Design

4.1 Overall Study Design

4.1.1 Overview of the Study

This is a multi-country, multi-center, open-labelled, randomized, controlled, extended phase III clinical trial. Totally 1440 healthy infants of 6 weeks old (42-47 days) for Bangladesh and of 6-8 weeks old (42-56 days) for Pakistan (Bangladesh and Pakistan, each includes 720 participants) are planned to be enrolled, and then randomized in a 1:1:1:1 ratio into four groups, i.e., co-administration group 1 (group C1), co-administration group 2 (group C2), staggered administration group 1 (group S1) and staggered administration group 2 (group S2).

Participants in group C1 and C2 will receive sIPV at 6,10,14 weeks old (at 4-week intervals), administered concomitantly with routine infant vaccine (may include Adsorbed Diphtheria-Tetanus-whole cell Pertussis-Hepatitis B and Haemophilus influenza type b conjugate vaccine (DTP-HepB-Hib), PCV or rotavirus vaccine in accordance with the local routine vaccination schedule). Participants in group S1 will receive sIPV at 6,10,14 weeks old, and receive routine infant vaccines at 8,12,16 weeks old (at 4-week intervals, respectively). Participants in group S2 will receive routine infant vaccines at 6,10,14 weeks old, and receive sIPV at 8,12,16 weeks old (at 4-week intervals, respectively). The sample size allocations, vaccination schedules and blood collections for each group

in different countries are shown in the tables (table 1 to table 3) below.

Table 1 Study Design for Each Group

Group	Sample Code	Size	Vaccination Schedule						Blood Collection Time	Antibody Tests Testing Item
			6 weeks	8 weeks	10 weeks	12 weeks	14 weeks	16 weeks		
C1	360	sIPV+			sIPV+			sIPV+	Baseline 18 Weeks	Neutralizing antibody against polioviruses of type 1,2,3
		Routine vaccines			Routine vaccines			Routine vaccines		
C2	360	sIPV+			sIPV+			sIPV+	Baseline 18 Weeks	Antibodies against Diphtheria, Tetanus, Pertussis (FHA, Pertactin, Pertussis toxoid), Hepatitis B, Hib, Pneumococcal antibodies*
		Routine vaccines			Routine vaccines			Routine vaccines		
S1	360	sIPV	Routine vaccines	sIPV	Routine vaccines	sIPV	Routine vaccines	sIPV	Baseline 18 Weeks	Neutralizing antibody against polioviruses of type 1,2,3
S2	360	Routine vaccines	sIPV	Routine vaccines	sIPV	Routine vaccines	sIPV	sIPV	Baseline 18 Weeks	Antibodies against Diphtheria, Tetanus, Pertussis (FHA, Pertactin, Pertussis toxoid), Hepatitis B, Hib, Pneumococcal antibodies*
Total	1440									

*Only for serotype 1, 5, 6B, 14, 19F.

Table 2 Vaccination Schedule for Bangladesh

Groups	Vaccination Schedule					
	6 weeks	8 weeks	10 weeks	12 weeks	14 weeks	16 weeks
C1&C2	sIPV		sIPV		sIPV	
	DTP-HepB-Hib		DTP-HepB-Hib		DTP-HepB-Hib	
	PCV10		PCV10		PCV10	
S1	sIPV	DTP-HepB-Hib	sIPV	DTP-HepB-Hib	sIPV	DTP-HepB-Hib
		PCV10		PCV10		PCV10
	DTP-HepB-Hib	sIPV	DTP-HepB-Hib	sIPV	DTP-HepB-Hib	sIPV
S2	PCV10		PCV10		PCV10	

Table 3 Vaccination Schedule for Pakistan

Groups	Vaccination Schedule					
	6 weeks	8 weeks	10 weeks	12 weeks	14 weeks	16 weeks
C1&C2	sIPV		sIPV		sIPV	
	DTP-HepB-Hib		DTP-HepB-Hib		DTP-HepB-Hib	
	PCV13		PCV13		PCV13	
S1	Rotavirus vaccine		Rotavirus vaccine		Rotavirus vaccine	
		DTP-HepB-Hib		DTP-HepB-Hib		DTP-HepB-Hib
	sIPV	PCV13	sIPV	PCV13	sIPV	PCV13
S2	Rotavirus vaccine		Rotavirus vaccine		Rotavirus vaccine	
	DTP-HepB-Hib		DTP-HepB-Hib		DTP-HepB-Hib	
	PCV13	sIPV	PCV13	sIPV	PCV13	sIPV

4.1.2 Immunogenicity Observation

About 3 ml venous blood will be collected before the first vaccination and 28 days (+7 days) after the last vaccination of sIPV or routine vaccines. Group C1 and S1 will be compared in terms of immunogenicity against polio, Group C2 and S2 will be compared in terms of immunogenicity against diphtheria, Tetanus, Pertussis, Hepatitis B, Hib and Pneumococcal.

4.1.3 Safety Observation

- For all participants, the immediate reactions within 30 minutes after each vaccination will be observed on site.
- Within 7 days after each vaccination, solicited selected AEs will be strictly recorded.
- Up to 28 days after the last dose vaccination, unsolicited AEs and any SAEs will be required to recorded.

4.2 Randomization

Stratified blocked randomization was carried out in this study, taking the study site as a stratification factor. The independent randomization statistician used SAS 9.4 to generate a randomization code list. In order to minimize the probability of relevant participants being informed of the group, the paper randomization card with numbers will be used. For each eligible participant, after enrollment, the grouping information will be revealed, including the name of the vaccine and the site of vaccination.

4.3 Sample Size Consideration

The sample size in this study is calculated based on the non-inferiority hypothesis of the immune response to sIPV, taking the combination vaccination group as the test group and staggered vaccination group as the control group. The sample size calculation parameters are as follows:

- The seroconversion rate of the control group is estimated as 90% referring to the previous clinical data of sIPV;
- The non-inferiority criterion is: the lower limit of 95% Confidence Interval (CI) of the difference between groups (test group-control group) $>-10\%$;
- The allocation ratio between test group and control group for immunogenicity evaluation against either polio of three serotypes is 1:1;
- The one-sided significance level is 0.025;
- The overall statistical power ($1-\beta$) is 80%, with a corrected statistical power of 93.3% ($1-20\% / 3$) for statistical test of each serotype.

Considering the conditions above, the sample size calculated by using PASS 2022 (V22.0.2) for each group is 233. Considering a dropout rate of approximately 15% and a blood collection failure rate of approximately 10%, sample size of 360 is determined for each group.

5 Endpoints

5.1 Immunogenicity Endpoints

➤ **In the comparison between group C1 and group S1**, the immunogenicity endpoints for neutralizing antibody (Nab) against polioviruses of serotype I, II, III at 28 days after last vaccination of sIPV will be defined as follows, respectively:

- (1) **Seroconversion (4-fold increase) rate**, which is defined as pre-vaccination Nab titer against polioviruses $<1:8$ and post-vaccination Nab titer against polioviruses $\geq 1:8$, or 4-fold Nab titer against polioviruses increase in case that pre-vaccination Nab titer against polioviruses $\geq 1:8$.
- (2) **Seroconversion Rate (SCR) in seronegative participants at pre-vaccination**, which is defined as pre-vaccination Nab titer against polioviruses $<1:8$ and post-vaccination Nab titer against polioviruses $\geq 1:8$.
- (3) **4-fold increase rate in seropositive participants at pre-vaccination**, which is defined as 4-fold Nab titer against polioviruses increase in case that pre-vaccination Nab titer against polioviruses $\geq 1:8$.
- (4) **Sero-Protection Rate (SPR)**, which is defined as Nab titer against polioviruses $\geq 1:8$.

(5) **Geometric Mean Titer (GMT) and Geometric Mean Fold Rise (GMFR)**, which is defined as the increase of Nab titers against polioviruses after vaccination compared to baseline.

(6) **GMT and GMFR in seronegative participants at pre-vaccination**

(7) **GMT and GMFR in seropositive participants at pre-vaccination**

➤ **In the comparison between group C2 and group S2**, the immunogenicity endpoints for Immunoglobulin G (IgG) antibody against Pertussis Toxin (PT), Filamentous Hemagglutinin (FHA) and Pertactin (PRN) at 28 days after last vaccination of DTP-HepB-Hib will be defined as follows, respectively:

- (1) **Seropositivity rate**, which is defined as IgG antibody concentration after vaccination ≥ 20 EU/ml.
- (2) **SCR**, which is defined as pre-vaccination IgG antibody concentration < 5 EU/ml and post-vaccination concentration ≥ 20 EU/ml, or 5 EU/ml \leq pre-vaccination IgG antibody concentration

<20 EU/ml and 4-fold concentration increase, or pre-vaccination IgG antibody concentration \geq 20 EU/ml and 2-fold concentration increase.

(3) Geometric Mean Concentration (GMC) and GMFR, which is defined as the increase of IgG antibody concentrations after vaccination compare to baseline.

➤ **In the comparison between group C2 and group S2**, the immunogenicity endpoints for IgG antibody against diphtheria, tetanus, Hepatitis B (HepB), Hib and pneumococcal (including serotypes of 1, 5, 6B, 14 and 19F) at 28 days after last vaccination of DTP-HepB-Hib will be defined as follows, respectively:

(1) SPR, which is defined as corresponding IgG antibody concentration after vaccination \geq cut off value.

(2) GMC and GMFR, which is defined as the increase of corresponding IgG antibody concentration after vaccination compare to baseline.

The cutoff values of above IgG antibodies are shown in Table 4.

Table 4 Cutoff Values of Different IgG Antibodies

Antibodies	Cutoff Values
Diphtheria	0.1 IU/ml
Tetanus	0.1 IU/ml
Hepatitis B	10 mIU/ml
Hib	0.15 μ g/mL
Pneumococcal*	0.35 μ g/mL

*The following serotypes will be detected in this study: 1, 5, 6B, 14, 19F

5.2 Safety Endpoints

(1) Adverse Events

➤ **Solicited Adverse Events:** including solicited local (vaccination site) and systemic AEs that occur during 7 days after each vaccination. The solicited local (vaccination site) AEs: including redness, swelling, rashes, induration and pruritus. The solicited systemic AEs: including fever, acute allergic reaction, diarrhea, decreased appetite, irritability, and decreased activity.

➤ **Unsolicited Adverse Events:** including all AEs except solicited AEs during the solicitation period, and all AEs during the non-solicitation period.

(2) Serious Adverse Events

6 Analysis Sets

(1) Full Analysis Set (FAS): Following the principle of Intention to Treat (ITT), it includes all participants who are randomized, complete at least one vaccination against the antigen to be evaluated, and have the valid immunogenicity results before the first vaccination. The participants who are vaccinated erroneously will be analyzed for the immunogenicity evaluation as randomized according to the ITT principle.

(2) Per Protocol Set (PPS): It is a subset of FAS which including all the participants who are eligible for this study according to the inclusion and exclusion criteria, and then randomized, complete full vaccination as protocol specified, and have valid immunogenicity results before and after the vaccination. Participants who meet the following conditions will be excluded from PPS:

- Those who has significant protocol deviations;
- Those who are vaccinated with the wrong vaccine;
- Use of protocol prohibited vaccines or drugs;
 - Other investigational or unlicensed products (drugs or vaccines);
 - Long-term use (lasting more than 14 days) of immunosuppressive or other immunomodulatory drugs (inhaled or topical steroids are allowed);
 - Immunoglobulin and/or blood preparations;
- Newly diagnosed autoimmune disease, including human immunodeficiency virus (HIV) infection;
- Other situations affecting the evaluation of vaccine immunogenicity.

For group C1 and S1, FAS and PPS will be defined for Nab against polioviruses of serotype I, II, III, respectively. For group C2 and S2, FAS and PPS will be defined for IgG antibodies of diphtheria, tetanus, pertussis (including PT, FHA and PRN), hepatitis B, Hib and pneumococcal (including serotypes of 1, 5, 6B, 14 and 19F), respectively.

(3) Safety Set (SS): All randomized participants who completed at least one dose vaccination will be included in the safety set. Participants who are vaccinated with the wrong vaccine will be analyzed for safety evaluation as treated according to All Subjects as Treated (ASaT) principle.

(4) Safety Set 1 for sIPV (SS1_sIPV) : All randomized participants who completed the 1st vaccination of sIPV will be included in SS1_sIPV. Participants who are vaccinated with the wrong

vaccine will be analyzed for safety evaluation as treated according to ASaT principle.

(5) Safety Set 2 for sIPV (SS2_sIPV): All randomized participants who completed the 2nd vaccination of sIPV will be included in SS2_sIPV. Participants who are vaccinated with the wrong vaccine will be analyzed for safety evaluation as treated according to ASaT principle.

(6) Safety Set 3 for sIPV (SS3_sIPV): All randomized participants who completed the 3rd vaccination of sIPV will be included in SS3_sIPV. Participants who are vaccinated with the wrong vaccine will be analyzed for safety evaluation as treated according to ASaT principle.

(7) Safety Set 1 for sIPV and routine vaccines (SS1_sIPV&Routine): All randomized participants who completed 1st vaccination of sIPV and routine vaccines will be included in SS1_sIPV&Routine. Participants who are vaccinated with the wrong vaccine will be analyzed for safety evaluation as treated according to ASaT principle.

(8) Safety Set 2 for sIPV and routine vaccines (SS2_sIPV&Routine): All randomized participants who completed 2nd vaccination of sIPV and routine vaccines will be included in SS2_sIPV&Routine. Participants who are vaccinated with the wrong vaccine will be analyzed for safety evaluation as treated according to ASaT principle.

(9) Safety Set 3 for sIPV and routine vaccines (SS3_sIPV&Routine): All randomized participants who completed 3rd vaccination of sIPV and routine vaccines will be included in SS3_sIPV&Routine. Participants who are vaccinated with the wrong vaccine will be analyzed for safety evaluation as treated according to ASaT principle.

7 Statistical Method

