9.2 Analysis Sets

Analysis sets for immunogenicity evaluation

Full analysis set (FAS), following the principle of intent to treat (ITT), including all subjects who are randomized, **complete at least one vaccination against the antigen to be evaluated**, and have the valid immunogenicity results before the first vaccination. The participants who are vaccinated erroneously will be analyzed for the immunogenicity evaluation as randomized according to the ITT principle.

Per-protocol set (PPS), a subset of FAS, including all the subjects who are eligible for this study according to the inclusion and exclusion criteria, and then randomized, complete full vaccination as protocol specified, and have valid immunogenicity results before and after the vaccination. Subjects who meet the following conditions will be excluded from PPS:

- 1) Those who has significant protocol deviations;
- 2) Those who are vaccinated with the wrong vaccine;
- 3) Use of protocol prohibited vaccines or drugs
 - Other investigational or unlicensed products (drugs or vaccines)
 - Long-term use (lasting more than 14 days) of immunosuppressive or other immunomodulatory drugs (inhaled or topical steroids are allowed)
 - Immunoglobulin and/or blood preparations
- 4) Newly diagnosed autoimmune disease, including human immunodeficiency virus (HIV) infection
- 5) Other situations affecting the evaluation of vaccine immunogenicity

Analysis sets for safety evaluation

Safety Set (SS): All randomized subjects who completed at least one dose vaccination will be included in the safety set. Subjects who are vaccinated with the wrong vaccine will be analyzed for safety evaluation as treated according to ASaT principle (All Subjects as Treated).

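### FAS and PPS require a baseline antibody result even for sero-protection and seropositivity, so some infants with these endpoints observed are dropped while the FAS keeps infants without them

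*SAP*

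**What the plan says.** - **FAS.** SAP section 6 takes randomised infants who "complete at least one vaccination against the antigen to be evaluated, and have the valid immunogenicity results before the first vaccination". Protocol 9.2 has the same condition ("have the valid immunogenicity results before the first vaccination"). Neither asks for a post-vaccination result.
- **PPS.** It is a subset of the FAS whose members "complete full vaccination as protocol specified, and have valid immunogenicity results before and after the vaccination".
- **Sets differ by antigen, not by endpoint.** "For group C1 and S1, FAS and PPS will be defined for Nab against polioviruses of serotype I, II, III, respectively"; the C2/S2 antigens are treated likewise. Each antigen has one FAS and one PPS for all its endpoints.
- **Endpoints without a baseline term (SAP 5.1).** Pertussis seropositivity is a rate "which is defined as IgG antibody concentration after vaccination ≥ 20 EU/ml". For diphtheria, tetanus, HepB, Hib and pneumococcal the wording is "SPR, which is defined as corresponding IgG antibody concentration after vaccination" at or above the cutoff. Polio sero-protection is a titre of at least 1:8. Protocol Table 5 agrees.
- **Populations.** SAP 7.7 analyses all of these on FAS and PPS only.
- **Missing values.** Protocol 9.6 and SAP 7.9 use LOCF. SAP 4.1.2 has two draws: before the first vaccination and 28 days after the last.

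**The concern.** Seroconversion, GMFR and the baseline-adjusted ANCOVA need a pre-vaccination value. A post-vaccination threshold does not. Because one pair of sets serves both kinds of endpoint, an infant with all three doses and a valid day-28 result contributes nothing to the rate if the 6-week sample failed. An infant never sampled after vaccination remains in the FAS. With two draws, the only value LOCF can carry is the baseline, so a pre-vaccination concentration is scored as a post-vaccination response.

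This matters most for diphtheria and tetanus sero-protection and PT/FHA/PRN seropositivity, which Protocol 9.3.4 tests for non-inferiority. What is at stake there is some precision, and a FAS that departs from its stated intention-to-treat principle by dropping observed outcomes.

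**Working it through.** **Inputs.** 360 per group, 15% dropout, about 10% blood-collection failure, 90% control rate, 10-point margin, one-sided 0.025, 93.3% power per serotype (Protocol 9.1, SAP 4.3). The 90% rate was set for polio seroconversion. The plan gives no planning rate for the C2/S2 antigens.

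**1. The plan's own figure.** A Farrington-Manning calculation with 90% in both arms and power 1 − 0.20/3 = 0.9333 gives 231.8, so 232 per group against the stated 233. The planning inputs are therefore read as intended. The point below does not depend on this figure.

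**2. Infants affected.** The 10% is not split between draws, so let f be the share falling at baseline. Assume failures and dropout are independent, dropout comes after the baseline draw, and every infant gets at least one dose.

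- Baseline missing: b = 1 − 0.9^f. Post draw failed: q = 1 − 0.9^(1−f).
- Post result available: 360 × 0.85 × (1 − q). Of these, lost for want of baseline: that number × b.
- FAS: 360 × (1 − b). FAS without a post result: FAS × [1 − 0.85 × (1 − q)].

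| f | b | Post result | Lost | FAS | FAS without post result |
|---|---|---|---|---|---|
| 0 | 0 | 275.4 | 0 | 360.0 | 84.6 |
| 0.5 | 0.0513 | 290.3 | 14.9 | 341.5 | 66.1 |
| 1 | 0.10 | 306.0 | 30.6 | 324.0 | 48.6 |

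In every row 360 × 0.85 × 0.90 = 275.4 infants have both samples.

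**3. Precision.** Take a less favourable reading than the plan's single rate, with 10% failing at each draw: 360 × 0.85 × 0.90 = 275 have the post result, and 275.4 × 0.90 = 248 have both.

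- Half-width at 90%, 1.96 × √(2 × 0.9 × 0.1/n): 5.01 points at n = 275 and 5.28 at n = 248, a difference of 0.27.
- Wald power at 90%, Φ(0.10/√(0.18/n) − 1.96): Φ(3.909 − 1.96) = 97.4% at 275 and Φ(3.712 − 1.96) = 96.0% at 248.
- At a 95% rate, power exceeds 99.9% for both.

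**4. What LOCF does to the infants kept.** SAP 7.1.1 uses non-missing participants as the denominator. That does not remove them, because LOCF makes them non-missing. The documents give no baseline positivity. As an illustration only, take an observed rate of 95%, 15% without a post sample, and baseline positivity of 10% to 70%. The FAS rate becomes 0.95 × 0.85 + 0.10 × 0.15 = 82% up to 0.95 × 0.85 + 0.70 × 0.15 = 91%.

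**The case against.** **One set per antigen is a reasonable convention.** The same antigens are also analysed by GMFR and ANCOVA, and pertussis by seroconversion. A common set keeps the same infants across tables. That is a real convenience, and the change gives it up. It does not make the baseline informative for a post-only threshold.

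**The loss may be negligible.** This stands. If baseline draws rarely fail, almost no one is lost.

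**A reader might infer a serious loss of power.** At an 80% rate in both arms, √(0.32/n) gives Φ(0.972) = 83.4% at 275 and Φ(0.824) = 79.5% at 248, which crosses 80%. The documents give no 80% response rate. At the plan's 90% the fall is 1.4 percentage points (97.4% to 96.0%).

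**A reader might infer bias,** since the trial is open-label and Protocol 8.6 lists the baseline draw after the randomisation number. The documents do not support that. Protocol 6.3 keeps those drawing blood unaware of group and the laboratory blinded. Protocol 8.1.2 provides a backup serum tube. The draw precedes vaccination, so its failure cannot result from vaccine response. No mechanism for different loss in C2 and S2 is evident.

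**Requiring a post result is also a post-randomisation restriction,** and it removes more infants (49 to 85 per group) than it regains (0 to 31). The counts are right. However, the infants removed have no observed endpoint and would enter only through a carried-forward baseline value, while those regained have one.

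**Conclusion.** The point holds as a mismatch between the analysis sets and the endpoints defined on the post-vaccination value alone. Under the plan's own 15% and 10% losses, 0 to about 31 infants per group with an observed endpoint are dropped, about 15 at an even split. The FAS meanwhile keeps 49 to 85 per group without one. These counts rest on independent losses and an assumed split of the 10%, which the documents do not give.

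The cost in precision is small: about 0.3 points of CI half-width at a 90% rate, even with 10% failing at each draw. Differential bias between groups is not shown. Primary seroconversion is unaffected, because it needs both samples. The correction is still worth making: it is cheap, every infant it adds has the endpoint observed, and it stops a pre-vaccination value from standing in for a post-vaccination response in the secondary non-inferiority comparisons.

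**What to change.** For sero-protection and seropositivity rates only:

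- In Protocol 9.2 and SAP section 6, define the FAS as randomised, at least one dose of the relevant vaccine, and a valid post-vaccination result, with no baseline requirement.
- Remove the baseline requirement from the PPS for the same endpoints.
- In Protocol 9.6 and SAP 7.9, state that baseline values are not carried forward for these endpoints.

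Leave the baseline requirement in place for seroconversion, GMFR and ANCOVA.

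The cost is revised wording and an endpoint-specific flag in the analysis data. Denominators will differ slightly between the rate tables and the GMFR/ANCOVA tables, and infants with no post sample leave the FAS for these rates. SAP 2.1 has the SAP finalised before database lock, so the change should be made by then.
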